5 STATISTICAL METHODS

All descriptive statistics for continuous variables will be reported using mean, standard deviation (SD), median, minimum and maximum unless otherwise specified. Categorical variables will be summarized as number (percentage) of subjects.

5.1 Study Endpoints

5.1.1 Primary Endpoint

The primary endpoint is mean change from baseline in the PPR range in each subject's most sensitive eye condition at each dose level of E2730 as compared to placebo.

5.1.2 Secondary Endpoints

- Mean changes from baseline in PPR ranges in each subject's eye closure, eyes closed, and eyes open condition at each dose level of E2730 as compared to placebo
- Onset, maximum change, and duration of photosensitivity response at each dose level in all 3 eye conditions at the time course of E2730 as compared to placebo
- Frequency and percentage of subjects with Complete Suppression, Partial Response, and no Response of PPR at each dose level of E2730 as compared to placebo
- Occurrence of AEs or changes in the neurological examination after single doses of E2730 compared to placebo
- Changes in vital signs, serum chemistries, complete blood counts, or liver function tests after single doses of E2730 compared to placebo

- PK of E2730 and its N-acetyl metabolite, M1
- Relationship between PK parameters of E2730 onset, maximum change, and duration of impact on photosensitivity

5.2 Study Subjects

5.2.1 Definitions of Analysis Sets

The Safety Analysis Set is the group of subjects who receive at least 1 dose of study drug and have at least 1 postdose safety assessment.

The Pharmacokinetic Analysis Set is the group of randomized subjects who receive at least 1 dose of study drug and have sufficient PK data to derive at least 1 PK parameter.

The Pharmacodynamic Analysis Set is the group of randomized subjects who receive at least 1 dose of study drug and have sufficient PD data to derive at least 1 PD parameter.

5.2.2 Subject Disposition

The number of subjects screened and the number failing screening (overall and by reason for failure) will be summarized. Screen failure data will be listed. The number of subjects randomized along with the number of subjects administered each dose of E2730 will also be presented.

Subjects who prematurely terminate their participation in the study will be summarized by their primary reason as well as any other reasons(s) for study termination.

5.2.3 Protocol Deviations

Major protocol deviations will be presented as a listing.

5.2.4 Demographic and Other Baseline Characteristics

Demographic and other baseline characteristics for the Safety Analysis Set will be summarized overall using descriptive statistics. Continuous demographic and baseline variables include age, height, and weight; categorical variables include sex, age group, race, and ethnicity.

Medical History

The number (percentage) of subjects in the Safety Analysis Set reporting a history of any medical condition, as recorded on the CRF, will be summarized overall. A subject data listing of medical and surgical history will be provided.

5.2.5 Prior and Concomitant Therapy

All investigator terms for medications recorded in the CRF will be coded to an 11-digit code using the World Health Organization Drug Dictionary (WHO DD). The latest version before database lock will be used for analysis. The number (percentage) of subjects who took prior and concomitant medications will be summarized by Anatomical Therapeutic Chemical (ATC) class, and World Health Organization Drug Dictionary preferred term (PT). Prior medications will be summarized overall and concomitant medications will be summarized by treatment group. Prior medications will be defined as medications that stopped before the dose of study drug in treatment period 1. Concomitant medications for a treatment group will be defined as medications that started after the date of the dose of study drug up to 28 days after the subject's dose or the next dose date in next treatment period which is earlier. All prior and concomitant medications will be presented in subject data listings.

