9.3.1 Inclusion Criteria

Subjects must meet all of the following criteria to be included in this study:

1. Male or female 18 to 60 years old at the time of informed consent.
2. A diagnosis and history of a PPR on EEG with or without a diagnosis of epilepsy.
3. Currently taking up to a maximum of 3 concomitant antiepileptic drugs (AEDs). If taking concomitant AED(s), the dose must have remained stable for at least 4 weeks prior to screening.
4. A reproducible IPS-induced PPR on EEG of at least 3 points on a frequency assessment scale (SPR) in at least 1 eye condition on at least 3 of the EEGs performed at Screening.
5. A body mass index (BMI) between 18 to 35 kg/m² and a total body weight greater than or equal to 45 kg at the time of Screening.
6. Agrees to refrain from strenuous exercise and alcohol consumption during the 24-hour period before Screening and during the 24-hour period prior to each treatment day.
7. Willing and able to comply with all aspects of the protocol.

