9.3.2 Exclusion Criteria

Subjects who meet any of the following criteria will be excluded from this study:

1. Females who are breastfeeding or pregnant at Screening or Baseline (as documented by a positive beta-human chorionic gonadotropin [β -hCG] (or human chorionic gonadotropin [hCG]) test with a minimum sensitivity of 25 IU/L or equivalent units of β -hCG [or hCG]). A separate baseline assessment is required if a negative screening pregnancy test was obtained more than 72 hours before the first dose of study drug.
2. Females of childbearing potential who:
 - a) Within 30 days before study entry, have had unprotected sexual intercourse and did not use a highly effective method of contraception (eg, total abstinence, an intrauterine device, a double-barrier method [such as condom plus diaphragm with spermicide], a contraceptive implant, an oral contraceptive, or have a vasectomized partner with confirmed azoospermia)
 - b) Do not agree to use a highly effective method of contraception (as described above) throughout the entire study period and for 28 days after study drug discontinuation. If

currently abstinent, the subject must agree to use a double barrier method as described above if she becomes sexually active during the study period or for 28 days after study drug discontinuation. Females who are using hormonal contraceptives must be on a stable dose of the same hormonal contraceptive product for at least 4 weeks before dosing and must continue to use the same contraceptive during the study and for 28 days after study drug discontinuation.

NOTE: All females will be considered to be of childbearing potential unless they are postmenopausal (amenorrheic for at least 12 consecutive months, in the appropriate age group and without other known or suspected cause) or have been sterilized surgically (ie, bilateral tubal ligation, total hysterectomy, or bilateral oophorectomy, all with surgery at least 1 month before dosing).

3. Male subjects who have not had a successful vasectomy (confirmed azoospermia) or they and their female partners do not meet the criteria above (ie, not of childbearing potential or practicing highly effective contraception throughout the study period and for 28 days after study drug discontinuation). No sperm donation is allowed during the study period and for 28 days after study drug discontinuation.
4. History of nonepileptic seizures (eg, metabolic, structural, or pseudoseizures) while on any antiepileptic medication(s).

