9.7.1.5 Prior and Concomitant Therapy

All investigator terms for medications recorded in the CRF will be coded to an 11-digit code using the World Health Organization Drug Dictionary. The number (percentage) of subjects who took prior and concomitant medications will be summarized by treatment group, Anatomical Therapeutic Chemical (ATC) class, and World Health Organization Drug Dictionary preferred term (PT). Prior medications will be defined as medications that stopped before the dose of study drug. Concomitant medications will be defined as medications that started after the date of the dose of study drug up to 28 days after the subject's dose. All medications will be presented in subject data listings.

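### Read literally, the SAP's prior and concomitant definitions leave out every drug already ongoing at the first dose, including all compliant background antiepileptic drugs

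*SAP*

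**What the plan says.** SAP 5.2.5 gives two definitions. The first looks only at when a drug stopped: "Prior medications will be defined as medications that stopped before the dose of study drug in treatment period 1". The second looks only at when it started: "Concomitant medications for a treatment group will be defined as medications that started after the date of the dose of study drug". The window for the second closes 28 days after that dose "or the next dose date in next treatment period which is earlier". Prior drugs are tabulated for all subjects together and concomitant drugs by treatment. The listing in that section covers drugs in these two classes.

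Protocol 9.7.1.5 uses the same start rule: "Concomitant medications will be defined as medications that started after the date of the dose of study drug up to 28 days" after the dose. Its listing is wider: "All medications will be presented in subject data listings".

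On background therapy, criterion 3 of Protocol 9.3.1 describes subjects as "Currently taking up to a maximum of 3 concomitant antiepileptic drugs (AEDs", and where such drugs are used, "the dose must have remained stable for at least 4 weeks prior to screening". Protocol 9.4.7 also calls these drugs concomitant and forbids any change to them during the study. Under Protocol 9.3.2, women using hormonal contraceptives "must be on a stable dose of the same hormonal contraceptive product for at least 4 weeks before dosing" and must stay on the same product throughout.

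**The concern.** One definition tests the stop date and the other tests the start date, so a drug that spans the first dose satisfies neither. In a trial of an antiepileptic drug, background AEDs are the co-medication a reader most wants to see. The concomitant medication table is the natural place to look, because the baseline variables named in SAP 5.2.4 do not mention AEDs (that list is not said to be exhaustive) and no other SAP section gives an AED summary. If 5.2.5 is programmed as written, the table would show no AED use in subjects the protocol itself describes as taking concomitant AEDs.

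The start rule also misattributes drugs across crossover periods. A drug begun in one period and continued is counted only under the treatment in which it began. A continuing drug begun on a dosing date is not credited to that day's treatment.

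**Working it through.** The plan states no figure here to reproduce. The check applies the two definitions to dates.

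**Inputs.** Doses fall on Days 1, 22 and 43 (SAP 8.2). Screening is Day −21 to Day −1 (Protocol 9.1.1.1). There is no Day 0.

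**Step 1: the windows.** Does the 28-day cap ever end the Period 1 or Period 2 window before the next dose? With visits 21 ± 3 days apart (Protocol synopsis), the longest gap is 21 + 3 = 24 days. With the Table 5 visit windows (22 ± 3 and 43 ± 3), it is 46 − 19 = 27 days. Both are below 28, so the next dose closes the window for any subject who receives one. At nominal days, a drug must start:

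- Period 1: after Day 1, up to Day 22
- Period 2: after Day 22, up to Day 43
- Period 3: after Day 43, up to Day 43 + 28 = Day 71

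SAP 5.2.5 does not say whether the closing dose date is inside the window.

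**Step 2: where background drugs fall.** The latest screening day is Day −1. Four weeks of stable dosing before that puts an AED's start no later than Day −1 − 28 = Day −29 (Day −49 if screened on Day −21). It may not change on study, so it continues past Day 1. A stable hormonal contraceptive started at least 28 days before dosing, so by Day −28, and also continues. Neither stopped before the Period 1 dose, so neither is prior. A start on or before Day 1 is not after Day 1, 22 or 43, so neither falls in any start window.

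**Step 3: cases.** The last column uses an overlap rule: taken at any time from the period's dose until the earlier of 28 days or the next dose.

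| Drug | As written | By overlap |
|---|---|---|
| AED, started by Day −29, ongoing | neither | Periods 1, 2, 3 |
| Hormonal contraceptive, started by Day −28, ongoing | neither | Periods 1, 2, 3 |
| Started Day −10, stopped Day 30 | neither | Periods 1, 2 |
| Started Day 1, ongoing | neither | Periods 1, 2, 3 |
| Started Day 10, ongoing | Period 1 only | Periods 1, 2, 3 |
| Started Day 22 after the dose, ongoing | Period 1 if the closing date is included, otherwise neither | Periods 2, 3 |
| Started Day 43 after the dose, ongoing | Period 2 if included, otherwise neither | Period 3 |
| Started Day −10, stopped Day −2 | prior | prior |

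A background AED thus counts in 0 of 3 periods as written and in 3 of 3 by overlap.

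**Step 4: size.** Each subject may take 0 to 3 AEDs. With 9 subjects that is 0 to 9 × 3 = 27 AED records, all unclassified if compliant. The 27 is not a firm ceiling: enrolment is approximate and subjects may be replaced. The documents give no expected AED use.

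**The case against.** The strongest reply is that the intent is obvious and a competent programmer would count ongoing AEDs as concomitant. Derivation rules and table shells sit in separate documents (SAP 9 and 11), so no wrong output has been shown. The protocol promises a listing of all medications, and with about 9 subjects such a listing would display each subject's AEDs. Counting a drug only where it started could also be a deliberate rule for newly started medication.

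Much of this stands: the defect is in the text, not in a known table, and its practical weight is small. Two parts do not stand. A silent correction would depart from the SAP's own definition, and the protection from the listing rests on the protocol, because the SAP sentence is narrower. A new-starts rule would be coherent only with a separate class for ongoing drugs. The SAP has none, and the protocol calls these AEDs concomitant.

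A reader might infer more than the documents support:

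- **That AED data are lost.** Protocol 9.4.7 records on the CRF all medication given during the study, from consent onward.
- **That the primary result is affected.** The model in SAP 5.5.2 and 13.2 uses treatment, period, sequence, baseline and subject, with no medication flag. Compliant AEDs are also constant across a subject's periods.
- **That every drug last taken on Day 1 is unclassified.** The prior definition refers to the dose, not the date, so a drug stopped on Day 1 before dosing is prior as written.

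**Conclusion.** The point holds as a definition error. Followed literally, SAP 5.2.5 puts no drug begun on or before Day 1 and continued past the Period 1 dose in either summary. That covers every protocol-compliant background AED and stable hormonal contraceptives. The SAP listing could omit the same drugs. Drugs begun on study and continued are under-counted in later periods, and a continuing drug begun on a dosing date is not credited to that day's treatment.

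The effect is confined to the descriptive medication summary and listing. The conclusion assumes a literal reading and nominal dosing days. The unseen programming specifications may already depart from the text. Severity: minor. Label: wrong as written.

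**What to change.** In SAP 5.2.5, replace the concomitant definition with: *Concomitant medications for a treatment are those taken at any time from that period's dose until the earlier of 28 days after the dose or the next period's dose, regardless of start date, including those started earlier and ongoing at the dose.* Leave the prior definition as it is. Restore the protocol's scope for the listing, so that all medications appear. Align Protocol 9.7.1.5 at the next amendment.

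The cost is a short edit to one SAP section and a revised derivation flag. No new data are needed, because the medication records are already collected on the CRF.

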The safety, tolerability, and PK of E2730 will be assessed. A full neurological examination and vital signs evaluation will be performed at screening and a brief neurological examination will be performed at predose and at scheduled time points after dosing. E2730 activity will be characterized by EEG-IPS, for a minimum of 2.5 minutes under all eye conditions (eye closure, eyes open, and eyes closed) on each treatment day. EEG-IPS sessions will be assessed on Day 1 (Visit 2), Day 22 (Visit 3), and Day 43 (Visit 4) at 30 minutes to 2 hours predose and 1, 2, 4, 6, and 8 hours postdose time points. The Columbia-Suicide Severity Rating Scale ([C-SSRS](#)) will be administered at screening, postdose at the end of every treatment visit, and at the Follow-up/Early discontinuation visit. Bond and Lader scale for central nervous system (CNS)-related sedative adverse effects will be measured for each subject at predose, 1, 2, 4, 6, and 8 hours postdose at every visit. There will be an interval of 21 ± 3 days between scheduled subsequent visits between dosing days.

After completing Treatment Period 3, all subjects will enter the Follow-up period during which they will be required to complete a Follow-up visit at 3 weeks ± 3 days following the last day of study product administration. The end of study is defined as the last subject completing the Follow-up Visit. The anticipated study participation duration for each subject is approximately 12 weeks.

Early Discontinuation

Subjects who discontinue study drug before completing all treatments in the study, for any reason,

will undergo an Early Discontinuation (ED) Visit within 3 weeks \pm 3 days of their last dose of study drug.
Number of Subjects Approximately 9 subjects will be randomized to achieve 6 evaluable subjects. Subjects who discontinue from the study early may be replaced, after consultation with the sponsor.

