8.2 Definitions of Treatment Periods

Treatment periods 1 to 3 are one-day treatment periods which will include single dose of study drug on Day 1 (Visit 2) for treatment period 1, Day 22 (Visit 3) for treatment period 2, and Day 43 (Visit 4) for treatment period 3.

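### SAP 5.2.5 never counts a drug started after dosing on a dosing day under that day's treatment, so the by-treatment concomitant medication table misplaces or omits it

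*SAP*

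**What the plan says.** SAP 5.2.5 sorts medications by date. On the prior side, "Prior medications will be defined as medications that stopped before the dose of study drug in treatment period 1", and these are summarised overall. On the concomitant side, "concomitant medications will be summarized by treatment group", by ATC class and preferred term.

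The concomitant window opens with "Concomitant medications for a treatment group will be defined as medications that started after the date of the dose of study drug up to" and closes at "28 days after the subject's dose or the next dose date in next treatment period which is earlier". The opening limit refers to the date of the dose, not to its clock time. The SAP does not say whether the closing date is itself included.

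SAP 8.2 describes the periods this way: "Treatment periods 1 to 3 are one-day treatment periods which will include single dose of study drug". The doses fall on Days 1, 22 and 43. The protocol synopsis fixes the spacing: "There will be an interval of 21 ± 3 days between scheduled subsequent visits between dosing days".

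Protocol 9.7.1.5 has the same strict opening limit, with a 28-day close and no cap at the next dose. The SAP added the cap for the crossover but left the opening limit as it was.

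**The concern.** A treatment period in this SAP is the dosing day. A window that opens only after the dosing date leaves the whole treatment period out of that treatment's own concomitant window. It may also hand that day to the treatment given about three weeks earlier.

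Dosing days are when all the postdose PPR readings are taken (1, 2, 4, 6 and 8 hours), and when a drug given for an acute event after dosing would be started. In sequence ABC, an adverse event after 120 mg on Day 43 belongs with 120 mg, while the drug given for it could be tabulated under 40 mg. The adverse event and concomitant medication tables could then not be read side by side.

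**Working it through.** The plan gives no figure to reproduce. The check applies the stated date rule to each dosing day.

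**Inputs**
- Dose dates: Days 1, 22 and 43 (SAP 8.2), with ±3 days on the second and third (Protocol Table 5).
- Spacing: 21 ± 3 days, that is 18 to 24 days (protocol synopsis).
- Opening limit: start date strictly later than the dose date (SAP 5.2.5).
- Closing limit: the earlier of dose date + 28 and the next dose date (SAP 5.2.5).

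**Rule.** With dose dates D1, D2, D3, a drug with start date d is counted under period i if D_i < d ≤ U_i, where U_i = min(D_i + 28, D_(i+1)) and U_3 = D_3 + 28.

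**Closing limits**
- Period 1: min(1 + 28, 22) = min(29, 22) = 22
- Period 2: min(22 + 28, 43) = min(50, 43) = 43
- Period 3: 43 + 28 = 71

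The windows are therefore Days 2–22, 23–43 and 44–71.

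**Starts after dosing on a dosing day.** For Day 22, 22 > 22 is false, so the drug is not counted under Period 2; 1 < 22 ≤ 22 is true, so it is counted under Period 1. Day 43 works the same way. A Day 1 start is in no window. It is not a prior medication either, because it cannot have stopped before the Period 1 dose.

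| Drug started after dosing on | Closing date included | Closing date excluded | Proposed rule |
|---|---|---|---|
| Day 1 | no treatment | no treatment | Period 1 |
| Day 22 | Period 1 treatment | no treatment | Period 2 |
| Day 43 | Period 2 treatment | no treatment | Period 3 |

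**Visit windows.** With the second dose on Day 19 to 25 and the third on Day 40 to 46 there are 7 × 7 = 49 combinations. The longest gaps are 25 − 1 = 24 and 46 − 19 = 27 days, both below 28, so the next dose date always sets the closing limit in Periods 1 and 2. All 49 combinations give the pattern in the table's inclusive column.

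**Where postdose starts in Periods 2 and 3 go, closing date included**
- 120 mg (4 sequence cells): counted as 40 mg in ABC and BCA, as placebo in ACB and BAC.
- Placebo (4 cells): counted as 120 mg in CAB and BCA, as 40 mg in BAC and CBA.
- 40 mg (4 cells): counted as placebo in ABC and CAB, as 120 mg in ACB and CBA.

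**Starts before dosing on Day 22 or 43.** These belong to the interval following the previous dose, and the inclusive reading puts them there.

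**Scale in the table.** If all of about 9 randomised subjects receive each treatment, one misplaced subject moves a percentage by 1/9, about 11 points.

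**The case against.** The strongest objections are these.

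- **Other SAP text points the right way.** SAP 5.3 says by-treatment summaries combine data from the period in which that treatment was given, and SAP 8.2 makes that period the dosing day. This shows what was probably intended. However, 5.2.5 states an explicit window for this one table, and a general sentence does not override it.
- **Derivation rules are deferred.** SAP 9 and 11 leave programming rules and table shells to separate documents, so same-day starts may be handled sensibly there. A program that did so would depart from the SAP as written.
- **The wrong-arm result depends on a reading.** It needs the closing date to be included. That is the ordinary sense, but the SAP does not say. Excluding it turns misplacement into omission. This stands, and it limits what can be claimed.
- **The table matters little.** It feeds no model, endpoint or interval. Protocol 9.7.1.5 lists all medications by subject. Protocol 9.4.7 bars changes to concomitant antiepileptic drugs and has the investigator record the adverse event for which a drug was given. With so few subjects, anyone asking whether a drug explains one day's PPR would go to individual data. This also stands.

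A reader might infer that every drug started on a dosing day is put in the wrong arm. The documents do not support that: predose starts on Days 22 and 43 are placed correctly on the inclusive reading, and Day 1 starts go to no arm at all.

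**Conclusion.** The point holds for drugs started after dosing. On either reading of the closing limit, SAP 5.2.5 never counts such a drug under the treatment given that day. With the closing date included, Day 22 and Day 43 starts appear under the previous treatment and Day 1 starts under none; with it excluded, all are missing from the table.

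The consequence is limited to the descriptive by-treatment concomitant medication table. A reader might infer that the PPR comparison is compromised. It is not: the mixed model uses treatment, period, sequence and baseline, and no medication data. The number of drugs affected cannot be derived from the documents and could be zero. Drugs already being taken before Day 1 are a separate matter.

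The conclusion rests on the wording of 5.2.5 being applied as written and on doses being less than 28 days apart, which the visit windows ensure. It is a small defect in a stated rule, worth correcting before unblinding.

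**What to change.** Replace the window in SAP 5.2.5 with:

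> Concomitant medications for a treatment are medications with a start date (and time, where recorded) on or after the dose in that period and before the earlier of the next period's dose or the end of 28 days after the dose. A drug started on a dosing day with no recorded time is assigned to the treatment given that day.

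The 28-day limit has to apply in every period, not only the third. Otherwise a subject who stops after Period 1 or 2 has no next dose and the window has no end.

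The cost is one sentence of SAP text and one changed date comparison in the program. There is a small downside: a predose start on a dosing day with no recorded time would be assigned to that day's treatment. Separating predose from postdose starts needs clock times, and the documents do not say whether these are recorded for medications.
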